Allogeneic HB-adMSCs, from a single qualified donor, is to be administered as an IV infusion. Each syringe will be provided by Hope Biosciences on the day of the infusion after all quality control essays have been performed and the results are within normal range.

Instructions for Administration

The designated study staff will administer the investigational product in the following manner:

- Prior to administration, visually inspect the infusion solution for particulates. If foreign particles are present, do not use the solution.
- Emergency equipment, such as epinephrine, antihistamines, and corticosteroids must be available in the event of infusion-related reactions.
- Start IV administration after dilution.
- Administer the infusion solution over a period of 1h. Observe the patient for at least 1-hour post-infusion for acute infusion-related reactions, including anaphylaxis. Continual monitoring will resume, with hospital staff observing vital signs, including blood pressure, pulse, or signs of rash/hives. Acute increase or decrease (30-40 mm/Hg from pre-infusion level) in blood pressure, an elevation of more than 20 BPM from baseline, or appearance of rash/hives would warrant review by PI.
- See Appendix 1 for guidelines on diagnosing anaphylaxis.
- Do not store or reuse any unused portion of the infusion solution. Any unused product or waste material should be disposed.
- Volume of study drug infused, start times, and stop times will be recorded. If any portion of the infusion (cell solution) is discarded, the reason will be recorded in the CRF.
- The patient will be monitored for a total of 2 hours from drug exposure to discharge.
 - a. During the Investigational product administration (1 hour) vital signs will be measured at minute 0, 15, 30 and 45.
 - b. Post infusion, vital signs will be measured at minute 0, 30, and 60.

Investigational Product Assignment (Randomization and Blinding)

Randomization

A total of 100 eligible subjects will be randomized to either placebo or treatment group within the associated study arm at baseline. Randomization will determine whether the subject receives placebo or HB-adMSCs.

A neutral, third-party personnel will be responsible for assigning the participants' treatment group. This role will be referred to as 'randomizer'. The designated personnel from the drug manufacturer will be responsible in labeling and packaging the investigational product for each

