participant. This role will be referred to as ‘mixer’. Participants’ names are not disclosed to the mixer and the unblinded information will only be known to the randomizer. Is with knowledge of bag contents will be the designated mixer.

Blinding for Clinical Evaluators

To minimize assessment bias, clinical evaluators (data analysts and physicians) will be trained on how to maintain blinding to treatment as best as possible. “Best as possible” means that blinding will be maintained unless an adverse event occurs that requires unblinding the physician, which is determined by the medical monitor or DSMB. Training includes review of the process of blinding, describing who will be responsible for assigning product for the appropriate group, labels that will be used to identify subjects but not treatment group, and the process that should be followed if an adverse event occurs, triggering review by medical monitor and/or DSMB.

Planned Unblinding

Unblinding of patient information will only occur in the case of adverse event suspected to be related to the investigational product, per the medical monitor and DSMB.

Regulatory authorities and/or the IRB may request the unblinding of data from one or more patients at any time.

Investigational Product Assignment and Infusion Schedule (Staggering)

Each patient will be allocated a unique subject number at screening and will retain this number throughout the study.

The Investigational Product is to be administered to all eligible, enrolled patients in Arm 1.1 and Arm 2.1 by intravenous infusion at a dose of 1×10^8 cells at days 0, 3, 7, and 10. Every effort should be made to adhere to the dosing schedule. However, a scheduled infusion should not be administered if a patient has an ongoing AE that, in the Investigator’s opinion, warrants holding the infusion.

Prior and concomitant conditions

The investigators should document all prior significant medical history. Additional conditions present at the time when informed consent is given and up to the time of first infusion (Day 0) are to be regarded as concomitant conditions. Illnesses first occurring or detected during the study and/or worsening of a concomitant condition during the study should be documented as AEs in the CRF. The exception is that results from COVID-19 testing will be added to the CRF as part of medical history.

Prior and concomitant medications

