All medications, including over-the-counter treatments and preventative vaccines taken by the patient during the study, including those treatments initiated prior to the start of the study, must be recorded in the CRF. The entry must include the dose, regimen, route, indication, and dates of use.

Study Procedures

Table 2 outlines the timing of procedures, and assessments to be performed throughout the study.

Table 2. Schedule of Assessments

Visit Number	1	2	3	4	5	6
Days	N/A	Day 0	Day 3	Day 7	Day 10	Day 28
Visit Name	Screening	Baseline/ Infusion 1	Infusion 2	Infusion 3	Infusion 4	End of Study / Telephone Encounter**
Window Period	Up to 7 days	±3 days	±3 days	±3 days	±3 days	±3 days
STUDY PROCEDURES						
Informed Consent	X					
Demographics	X					
Inclusion and Exclusion Criteria	X					
Medical History Review	X	X	X	X	X	X
Concomitant Medication Review	X	X	X	X	X	X
Eligibility	X					
Randomization	X					
Adverse Event Monitoring		X	X	X	X	X
ASSESSMENTS						
Vital Signs	X	X	X	X	X	
Weight and Height ¹	X	X	X	X	X	
Physical Examination	X	X	X	X	X	
Ordinal Scale		X	X	X	X	X
CBC with differential	X	X	X	X	X	
Comprehensive Metabolic Panel	X	X	X	X	X	
Coagulation Panel	X	X	X	X	X	
Urinalysis with pregnancy test (childbearing age women only)	X					
PCR test for SARS-CoV-2		X	X	X	X	
Exploratory Laboratory Assessments ²		X	X	X	X	
Inflammatory Marker Laboratory Assessments ³		X	X	X	X	
EKG		X*	X*	X*	X*	
CT Scan		X				X
Chest X Ray (PA, Single View) ⁴		X				X
ADMINISTRATION						
Allogeneic HB-adMSCs Administration		X	X	X	X	

1. Height will only be measured at screening

2. Exploratory laboratory Assessments: Natural Killer Cell Surface Antigen (CD3-CD56+ Marker Analysis), Troponin, Myoglobin, Creatine Kinase (CK) MB, Serum ferritin, CD4+/CD8+ ratio, D-dimer

3. Inflammatory Marker Laboratory assessments: CRP, IL-6, IL-10, TNFa

4. Chest Xray and CT scan will be performed as scheduled, however, if the patient is discharged prior to the scheduled tests at 28 days, any imaging (CT/Xray) done at discharge

* Subsequent EKG will be performed if necessary, such as abnormal result at baseline

** Telephone encounter is conducted if subject has been discharged

Informed Consent (ICF)

Prior to commencement of any trial related activity, the investigator or designated staff will obtain written informed consent from the patient or their Legally Authorized Representative (LAR).

Patient Re-Screening

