- **Not Related:** The adverse event is clearly not related to the investigational product. - i.e. another cause of the event is most plausible; and/or a clinically plausible temporal sequence is inconsistent with the onset of the event and the study intervention and/or a causal relationship is considered biologically implausible.

Investigator Reporting: Notifying the Study Sponsor

Any study-related unanticipated problem posing risk to subjects or others, and any type of serious adverse event, will be reported to Hope Biosciences Stem Cell Research Foundation (Sponsor) by telephone within 24 hours of the event. To report such events, a Serious Adverse Event (SAE) form will be completed by the investigator and electronically faxed to the sponsor within 24 hours to [contact]. The investigator will keep a copy of this SAE form on file at the study site.

Within the following 48 hours, the investigator will provide further information on the Serious Adverse Event or unanticipated problem in the form of a written narrative. This should include a copy of the completed Serious Adverse Event form, and any other diagnostic information that will assist the understanding of the event. Significant new information on ongoing Serious Adverse Events should be provided promptly to Hope Biosciences Stem Cell Research Foundation.

Routine Study Close-out

The study will end when Hope Biosciences Stem Cell Research Foundation has obtained all data necessary to complete its studies of the investigational product. Standard procedures may include, but is not limited to, review of regulatory documents, collection of completed case report forms, reconciliation of study records, removal or destruction of ancillary study supplies,

and informing the Investigator of remaining obligations (e.g., record retention, final report submission to the IRB, financial disclosure updates, etc.).

Infusion Stopping Rules

Infusion will be stopped when:

- Allergic reaction is aroused after the product has been administered intravenously.
- Patient verbally decline the treatment at any moment prior, or during the infusion.
- Hyperpyrexia develops after infusion administration begins (core body temperature greater than or equal to 40°C) [59].
- PI may stop the study at any time, based upon PI's discretion
- Systolic blood pressure (sbp) ≥ 170 or diastolic blood pressure (dbp) ≥ 90 and sbp ≤ 90 or dbp ≤ 60
- Sudden Severe Hypotension (30-40 mm/Hg drop from pre-infusion level)

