- Elevation or decrease in pulse of 20 bpm or more from baseline
- Change from baseline respiration rate in non-ventilated subjects

Study Alteration Rules

If any of the following events listed below occur, administration of the study drug will be immediately suspended. The Internal Monitoring Committee (IMC), presided by the Medical Monitor will meet to review the incident and its etiology. The committee determine if it is likely related to the drug, the infusion or unrelated. If the IMC along with the Medical Monitor agree that the SAE is unlikely or unrelated to the drug, the study will be continued. If the SAE appears to be definitely drug-related, the study will be stopped. If the SAE is probably or possibly linked to the drug, the IMC will determine the risk to future patients and decide if the study should proceed or be stopped.

Study Stopping Rules

The stopping rules listed below will trigger cessation of enrollment and potential study closure pending a comprehensive DSMB safety review.

1. Any infusion related death, deemed by PI to be associated or possibly associated with study drug.
2. Three or more of the same Grade 3 or higher AEs (judged by the investigator, medical monitor or sponsor), including infusion site reactions.
3. Any event which, in the opinion of the investigator, medical monitor or sponsor, contraindicates further dosing of additional subjects.
4. An infusion related, sustained (over 1 minute) episode of hypoxia (SaO₂ of less than 80%).
5. Any Grade 4-5 Adverse Event as defined in the NCI CTCAE v4.0 and determined to be temporally related to the HB-adMSC infusion by the Medical Safety Monitor and/or DSMB.

After such review, resumption of dosing may be considered, including consideration for any prophylactic interventions (e.g. antihistamines or corticosteroids for injection site reactions).

Medical Monitoring

Medical Monitor

It is the responsibility of the Principal Investigator to oversee the safety of the study at his/her site. This safety monitoring will include careful assessment and appropriate reporting of adverse events as noted above. At Hope Biosciences Stem Cell Research Foundation, [name], MD [contact] will be responsible for reviewing any reported AEs and SAEs to determine if changes to the study need to be made or if the study should be stopped for the protection of patients.

Data Safety Monitoring Board

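### The 20 bpm pulse limits for infusions are measured from baseline, the protocol's label for Day 0, so at infusions 2 to 4 they can shift with drift in resting pulse; the adjoining respiration line has no threshold

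*Protocol*

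**What the plan says.** The Protocol's Infusion Stopping Rules list events that require an infusion to be stopped. One is a pressure criterion, "Sudden Severe Hypotension (30-40 mm/Hg drop from pre-infusion level"). The next is pulse: "Elevation or decrease in pulse of 20 bpm or more from baseline". After that comes any change from the baseline respiration rate in patients who are not ventilated, with no figure attached.

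Instructions for Administration makes the same split within one sentence. An acute pressure change is judged against the pre-infusion level, but for pulse the text is "an elevation of more than 20 BPM from baseline, or appearance of rash/hives would warrant review by PI". This criterion covers rises only and leads to review, not to a stop.

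The same section supplies a same-day reading. During the administration hour "vital signs will be measured at minute 0, 15, 30 and 45". A second minute 0 follows: "Post infusion, vital signs will be measured at minute 0, 30, and 60".

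Infusions are given as "cells at days 0, 3, 7, and 10". Table 2 labels the Day 0 visit "Baseline/ Infusion 1", and the Day 0 procedures carry the same label in their heading. The Protocol's list of vital signs (Vital Signs, Height, and Weight) includes pulse but not respiratory rate. Respiratory Risks plans respiratory rate and work of breathing for the two hours after infusion.

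**The concern.** A rule meant to detect a reaction to an infusion should compare the patient with his or her own state just before that infusion. The pressure-change criteria do so. The pulse criteria use a different word, in two places, each time beside a criterion that uses the clearer term. That contrast invites staff to think a different reference is meant, and the protocol's visit label points to Day 0.

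On that reading the reference is nominally 3, 7 and 10 days old at infusions 2, 3 and 4, and drift in resting pulse counts as if it were an acute change. A patient whose pulse has settled would need a larger acute rise before the line fires, and could be stopped for a small fall or for no reaction at all. A patient whose pulse has drifted up would face the reverse. Two sites could also apply the same line differently.

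The respiration line is a problem whichever reference is used. Without a threshold, a change of one breath per minute meets a mandatory stop, and no scheduled pre-infusion rate exists to measure the change from.

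**Working it through.** **1. What baseline means in the documents.**

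- Protocol, Table 2 and the Day 0 procedures: the label of the Day 0 visit.
- Protocol, Screening: laboratory samples taken at screening are said to set a baseline (laboratory values only).
- Protocol, Coagulation Cascade: baseline is listed separately from screening, infusion and follow-up visits.
- Protocol, Appendix 1: an acute pressure fall is judged against the person's own baseline, with no visit named.
- SAP 5.3: for endpoints, the latest pre-treatment visit with a value, normally Day 0. SAP 8.3 summarises vital signs as change from baseline.

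None of these is tied to the infusion rules. The SAP definition governs analysis, not bedside decisions.

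**2. The pulse limits under each reading.** The protocol gives no derivation of the 20 bpm limit, so there is no planned figure to reproduce. Let

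- d = Day 0 pulse minus pulse at minute 0 of the current infusion (positive if the pulse has settled);
- a = acute change from minute 0 (positive for a rise).

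The current pulse minus the Day 0 pulse is then a − d.

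- Minute-0 reading: stop if |a| ≥ 20.
- Day 0 reading: stop if |a − d| ≥ 20, that is, a rise of at least 20 + d or a fall of at least 20 − d.

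| d (bpm) | Rise needed, Day 0 reading (20 + d) | Fall needed, Day 0 reading (20 − d) |
|---|---|---|
| −20 | 0 (met at the start) | 40 |
| −10 | 10 | 30 |
| 0 | 20 | 20 |
| 10 | 30 | 10 |
| 20 | 40 | 0 (met at the start) |

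On the minute-0 reading every row is 20 and 20.

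In whole bpm at d = 10, the readings disagree for acute rises of 20 to 29 (stopped only on the minute-0 reading) and acute falls of 10 to 19 (stopped only on the Day 0 reading).

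The PI-review criterion is a rise of more than 20. On the Day 0 reading it becomes a > 20 + d. At d = 10, rises of 21 to 30 are not reviewed; at d = −10, rises of 11 to 20 are added.

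At infusion 1, d = 0 if the Day 0 pulse used is the one taken just before it starts, and the readings coincide.

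**3. Frequency.** The documents give no pulse data. Suppose d is normal with mean m and SD s. The chance that the stop is already met at minute 0 is 1 − [Φ((20 − m)/s) − Φ((−20 − m)/s)]. With assumed m from 0 to 15 bpm and s from 8 to 15 bpm, this runs from 1.2% (m = 0, s = 8) to 37.9% (m = 15, s = 15). Those inputs are assumptions, and the width of the range shows only that no frequency can be stated.

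**4. Respiration.** With no threshold, the condition is any non-zero change. The Protocol's Adverse Events section also counts a change from baseline respiratory rate as an adverse event, so it presupposes a baseline rate. The vital-sign list omits respiratory rate, and the one plan to monitor it is after infusion. No section schedules a value before infusion.

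**The case against.** The strongest reply is that staff would not read the pulse rule against Day 0. It governs a running infusion, the review sentence opens with acute pressure changes, and a minute-0 pulse is in hand every time. Nothing tells staff to look up a Day 0 value. Appendix 1 shows the protocol using baseline for an acute reaction without meaning a visit. The extreme rows of the table count against the Day 0 reading too: a rule for stopping an infusion makes little sense if it is met before the infusion starts. All of this stands, and it is why the pulse point is conditional. It does not remove the ambiguity, because the text uses a different word from the adjoining criteria and the protocol attaches that word to Day 0.

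A reader might infer that SAP 5.3 settles the matter in favour of Day 0. It does not. That text covers endpoints, and the SAP is a draft dated November 2022, more than two years after the June 2020 protocol, so it cannot show what the protocol's authors meant.

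It can also be said that a fixed Day 0 reference would catch cumulative change over four doses, in a trial that names venous thromboembolism and right heart strain as risks. That stands as a real cost of the fix.

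Finally, respiratory rate is not wholly unmonitored, since Respiratory Risks plans it after infusion. That is correct, but it supplies neither a pre-infusion reference nor a threshold.

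**Conclusion.** The point holds as a minor one. For pulse, the literal wording shifts the limits at infusions 2 to 4 by exactly the drift since Day 0: 10 bpm of settling turns limits of 20 each way into a rise of 30 or a fall of 10. This rests on staff using Day 0; on minute 0 the effect is nil. Which reading the sites used, and how far pulses drifted, cannot be learned from the documents. The respiration line needs no such condition: as written, any change requires a stop.

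A reader might infer that infusion safety monitoring fails. The documents do not support that. Stops for allergic reaction, hyperpyrexia, pressure limits and a sudden pressure drop remain, as do PI discretion, review for rash or an acute pressure change, post-infusion respiratory monitoring, and a study-stopping rule for sustained hypoxia.

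A reader might also infer bias in the efficacy results, because the efficacy set requires all four infusions. That would need the Day 0 reading to be in use and the resulting stops to differ between arms; the documents show neither. No sample size, error rate or power figure is affected.

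**What to change.** **Pulse.** In Infusion Stopping Rules and in Instructions for Administration, replace the reference to baseline with: from the pre-infusion level (minute 0 of the administration hour) of the same infusion. Name the administration hour, because the post-infusion schedule has its own minute 0. The limits are then 20 bpm at all four infusions whatever the drift. This is wording in two places and needs no new measurement.

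The cost is that the line no longer fires for a pulse that has drifted up since Day 0. That is left to two existing provisions: recording a clinically significant vital sign as an adverse event (Vital Signs, Height, and Weight), and the dosing rule that "a scheduled infusion should not be administered if a patient has an ongoing AE that" in the investigator's opinion warrants holding it. Both rely on judgement. If the sponsor does want a Day 0 trigger, it should be a separate, explicitly labelled line.

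**Respiration.** Use the same pre-infusion reference, have the medical monitor set a numeric threshold (the documents give none), and record respiratory rate at the existing minute 0, 15, 30 and 45 vital-sign times. The cost is one threshold and one added reading at times when staff are already at the bedside.

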Patients will receive four intravenous infusions of 100 million HB-adMSCs throughout the entire duration of the study.

Arm 2 (placebo) (n=40)

Patients will receive four intravenous infusions of placebo (saline solution) throughout the entire duration of the study.

Safety assessments will be ongoing. Safety tests will include EKG, Complete Blood Count with differential, Complete Metabolic Profile (to include renal function and hepatic function) and Coagulation Panel screening for hepatotoxicity, cytopenias, renal failure or alterations in the coagulation cascade that might entail a safety concern for the individual. Efficacy will be measured by change from baseline in inflammatory markers (IL-6, CRP, IL-10, TNF-alpha), change from baseline in oxygenation, and time to receive negative PCR test result, change from baseline in exploratory markers (D-dimer, myoglobin, troponin, creatinine kinase, serum ferritin, CD3CD56, CD4/CD8, VEGF), time to return to room air (RTRA), change from baseline chest x-ray, change from baseline CT scan, and change from baseline in 7-point ordinal scale.

Selection and Withdrawal of Patients

Inclusion Criteria

1. Men, and women, over 18 years of age inclusively.
2. Suspected COVID-19 infection
3. Provides consent or consent is given by their legally authorized representative (LAR)
4. Agrees to the collection of venous blood per protocol.

Exclusion Criteria:

1. Pregnancy, lactation and those who are not pregnant but do not take effective contraceptive measures, in women of childbearing age.
2. Patients who have participated or are participating in a clinical trial of an experimental vaccine for SARS-CoV-2 or coronavirus during the study or within 30 days.
3. Inability to provide informed consent or to comply with test requirements.

4. Any medical disease or condition that, in the opinion of the site Principal Investigator or sub-investigator, precludes study participation. Including acute, subacute, intermittent or chronic medical disease or condition that would place the subject at an unacceptable risk of injury, render the subject unable to meet the requirements of the protocol, or may interfere with the evaluation of responses or the subject's successful completion of this trial.

Withdrawal, Removal, and Replacement of Patients

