If a patient is screened and fails to meet any study entry criteria or falls outside the screening window, they may be re-screened only once. Such patient must be fully consented a second time before the second set of screening assessments take place and shall be assigned a new subject number. Investigator discretion should be exercised in determining who may be re-screened.

In case of doubt about the accuracy of screening laboratory value(s), the laboratory test(s) may be repeated provided that this can be done within the 7-day screening period without the need to repeat all other screening procedures (i.e., no re-screening).

If a patient is enrolled after they have been re-screened, such subject shall be assigned a new subject ID number, different from the previous attempt to enroll.

Assessments by Week

Assessments will occur as outlined in the following subsections. For visits at Day 0 through 28 days, there will be a window of ± 3 days.

Screening

The Screening visit will last up to 7 days. Results from laboratory samples collected in this visit will set a baseline. These are the procedures to be performed during this visit:

- Written Informed Consent will be obtained from the subject or their legally authorized representative (LAR).
- COVID-19 confirmatory test results may be in progress during the screening period.
- Demographic Information will be obtained.
- Medical History and Current conditions will be obtained,
- Concomitant Medications will be obtained. Every medication listed should match a condition in the medical history.
- Vital signs will be obtained.
- Weight and Height will be measured.
- A physical exam will be performed.
- Blood and urine samples will be collected for laboratory assessments (CBC with differential, chemistry, and coagulation, pregnancy if appropriate).
- Ascertain patient eligibility by evaluating patient results against the inclusion/exclusion criteria.

Upon completion of all Screening procedures, the Principal Investigator must confirm and document the patient eligibility in the “Screening Result” CRF.

Infusion #1 - Day 0 (Baseline)

- Weight will be measured
- Vital Signs will be measured.
- Concomitant medications will be reviewed and updated if necessary.

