- Medical History will be reviewed and updated if necessary. This includes recording results of COVID-19 testing. If the patient reported a medication which does not match the current medical history, further investigation will be required to determine whether it was an Adverse Event, or the patient just forgot to mention it before. If it is found to be an AE, it should be recorded in the appropriate CRF. If the patient forgot to mention it before, a note to file (NTF) should be made to clarify the case.
- A PCR analysis to detect SARS-CoV-2 virus will be performed with a nasal swab
- Blood samples will be collected for laboratory assessments.
- Ordinal Scale to be performed.
- Administer investigational product.
- Monitor for AEs. Observe the patient for at least 1 hour after infusion for symptoms of infusion-related reactions and allergic reactions, including anaphylaxis (See Appendix 1).
- Instruct the patient on recognition of delayed serious allergic reactions, including anaphylaxis and seeking for medical assistance.
- Chest X-ray will be performed or collected from hospitalization due to COVID-19.
- CT scan will be performed or collected from hospitalization due to COVID-19.

Infusion # 2 (Day 3) and #3 (Day 7) and #4 (Day 10)

- Weight will be measured
- Vital Signs will be measured.
- Concomitant medications will be reviewed and updated if necessary.
- Medical History will be reviewed and updated if necessary. This includes recording results of COVID-19 testing. If the patient reported a medication which does not match the current medical history, further investigation will be required to determine whether it was an Adverse Event, or the patient just forgot to mention it before. If it is found to be an AE, it should be recorded in the appropriate CRF. If the patient forgot to mention it before, a note to file (NTF) should be made to clarify the case.
- A PCR analysis to detect SARS-CoV-2 virus will be performed with a nasal swab
- Blood samples will be collected for laboratory assessments.
- Ordinal Scale to be performed.
- Administer investigational product.
- Monitor for AEs. Observe the patient for at least 1 hour after infusion for symptoms of infusion-related reactions and allergic reactions, including anaphylaxis (See Appendix 1).
- Instruct the patient on recognition of delayed serious allergic reactions, including anaphylaxis and seeking for medical assistance.

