A Data Safety Monitoring Board (DSMB), consisting of three individuals appointed by a third-party contractor, will meet as scheduled by this protocol to review safety throughout study conduct. Specifically, the DSMB will meet to assess the progress of the first five patients with mild symptoms after their second infusion, and a decision on continuation of study will be made prior to the third infusion (day 7). The same will occur for the first five patients experiencing severe symptoms after their second infusion, and a decision on continuation of study will be made prior to their third infusion (day 14). All other patients may be screened beforehand so that enrollment may occur once the committee declares it may resume. DSMB is scheduled for at least 3 meetings pertaining to this protocol: after the mild symptom group receives their second infusion, after the severe symptom group receives their second infusion, and at study midpoint. Additional meetings may be necessary, upon request from the Medical Monitor.

DSMB will review all deaths (to assure non-attribution), cases of anaphylaxis or suspected anaphylaxis, thromboembolic events, new malignancy/tumor, infections/hospitalizations (including unrelated to COVID-19 but due to underlying condition). DSMB will also review safety data at mid-point of the study.

Risks

Potential Risks of the Investigational Product and Clinical Investigation

Risks Associated with HB-adMSCs

Respiratory Risks:

A potential risk is that the infusion could initiate a VTE event with subsequent

cardiopulmonary sequelae of respiratory failure and/or right heart strain/failure. We plan to monitor oxygen saturation, and respiratory rate/work of breathing for the first 2 hours post-infusion. The patient will be examined for VTE events (clinical exam, oxygen saturation) during each infusion visit and at each follow-up visit.

Hepatic Risks:

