## 2.2. Study Design

Overview of Study Design and Key Features	
Randomized, double-blind, placebo-controlled, parallel group study	
Design Features	

• Randomized, double-blind, Placebo controlled study.

• 100 Subjects

• 2 Treatment groups

▪ Group 1 → HB- adMSCs

▪ Group 2 → Placebo

• Duration of treatment: up to 7 days, and overall study includes screening (up to 7 weeks prior to randomisation), and 4 treatment visits after randomisation scheduled at Infusion 1 (Day 0), Infusion 2 (Day 3), Infusion 3 (Day 7), and Infusion 4 (Day 10). Follow-up at day 28 (EOS).

Dosing	

• HB- adMSCs (Hope Biosciences adipose derived mesenchymal stem cells) is to be administered as an IV infusion with a dose of 100 million cells

• Placebo is to be administered as an IV infusion. Contains Saline solution 0.9%

Treatment Assignment	

• Participants will be randomised 3:2 to receive HB-adMSCs active treatment or Placebo.

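### The DSMB section labels the severe cohort's third infusion Day 14, a day on which no schedule in the documents places any infusion

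*Protocol*

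**What the plan says.** The Data Safety Monitoring Board section sets up two early reviews, each of five patients after their second infusion. For the mild group, "a decision on continuation of study will be made prior to the third infusion (day 7". For the severe group, "a decision on continuation of study will be made prior to their third infusion (day 14". Each closing figure is a parenthetical label on the third infusion. The same section lists at least three meetings. It ties the first two to each group's second infusion, without a day, and the third to the study midpoint. It also holds enrolment of other patients until the board releases it.

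The infusion days are given in four places, always the same and always for every patient:

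- Protocol, Investigational Product Assignment and Infusion Schedule: "cells at days 0, 3, 7, and 10".
- Protocol, Table 2: infusions 1 to 4 at Days 0, 3, 7 and 10.
- Protocol, visit procedures: "Infusion # 2 (Day 3) and #3 (Day 7) and #4 (Day 10".
- SAP section 2.2: "Infusion 1 (Day 0), Infusion 2 (Day 3), Infusion 3 (Day 7), and Infusion 4 (Day 10".

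The Synopsis gives a maximum treatment duration of about 10 days. On timing tolerance, the protocol says: "For visits at Day 0 through 28 days, there will be a window of ± 3 days".

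On arms, the dosing text sends the product to "all eligible, enrolled patients in Arm 1.1 and Arm 2.1 by intravenous infusion". The Investigational Plan and SAP section 5.2 define only Arm 1 (cells) and Arm 2 (placebo). For Arm 2 the Investigational Plan says: "Patients will receive four intravenous infusions of placebo (saline solution) throughout the entire duration of the study".

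**The concern.** The review exists to let the board look at a few patients after two infusions and decide whether they, and the study, should go on to a third. It does that only if it happens before the third infusion. The protocol describes itself as the source of the board's meeting schedule, so a wrong day in this section can end up in the board's calendar. The label on the mild cohort agrees with the schedule and the label on the severe cohort does not, so a reader cannot tell when the severe review is due.

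At stake is whether the severe patients in this first group receive their last two infusions before anyone has reviewed the first two. The protocol's own Risks section names venous thromboembolism, with respiratory failure or right heart strain, as a potential infusion risk. Endpoints and efficacy analyses are not directly touched.

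**Working it through.** This is a comparison of dates; no sample-size or power formula applies.

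**Inputs.** Infusion days 0, 3, 7 and 10 (protocol dosing text, Table 2, visit procedures; SAP 2.2). Window ±3 days (Table 2 and Assessments by Week). Day labels 7 (mild) and 14 (severe) from the DSMB section. 100 million cells per active infusion, and allocation 60:40 (Investigational Plan; 3:2 in SAP 2.2).

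**Step 1: test the labels against the schedule.**

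| Cohort | Label on infusion 3 | Scheduled infusion 3 | Difference |
|---|---|---|---|
| Mild | Day 7 | Day 7 | 7 − 7 = 0 |
| Severe | Day 14 | Day 7 | 14 − 7 = 7 days |

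The mild label reproduces and the severe label does not. Day 14 is also 14 − 10 = 4 days after the scheduled fourth infusion.

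**Step 2: apply the window.**

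| Infusion | Nominal day | Window |
|---|---|---|
| 3 | 7 | 7 − 3 = 4 to 7 + 3 = 10 |
| 4 | 10 | 10 − 3 = 7 to 10 + 3 = 13 |

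The latest in-window third infusion is Day 10. The latest in-window fourth is Day 13, which is 14 − 13 = 1 day before the label. The window does not reconcile the two.

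**Step 3: time between infusion 2 and the labelled infusion 3.** The schedule gives 7 − 3 = 4 days to convene and decide. The severe label implies 14 − 3 = 11 days.

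**Step 4: exposure under each reading, for a patient on schedule.**

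| Reading | Infusions before the decision | Cells, active arm |
|---|---|---|
| Event wording governs | 2 | 2 × 100 = 200 million |
| Day label is followed | 4 | 4 × 100 = 400 million |

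The difference is two additional infusions per patient, or at most 5 × 2 = 10 infusions in the cohort. If the five are allocated in the overall ratio, about 5 × 60/100 = 3 would be on cells, so about 6 of the 10 infusions would be active. In so small a group the actual number on cells could be anything from 0 to 5.

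**Step 5: could Day 14 be a study-calendar day?** If the severe cohort started on study day 7, its third infusion would fall on 7 + 7 = 14. The arithmetic works, but no section states such a start or such a calendar.

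**The case against.** The strongest reply is that the sentence does not date the decision at all. The parenthesis describes the infusion, and the decision is required before that infusion. The section ties the review to events throughout: after the second infusion, before the third, and again in the meeting list with no day attached. On those words the gate works as intended. This stands. A reader might infer that the board's decision is fixed at Day 14 and so must come too late; the text does not support that. It comes late only if someone plans by the label and passes over the words around it.

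The study-calendar reading is a second reply. The dosing section's heading mentions staggering, and enrolment is held between reviews, so a later start for the severe cohort is conceivable. It remains an assumption, and the mild label matches the per-patient schedule without it.

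Third, the reach is limited. Other enrolment is held under either reading, the infusion and study stopping rules and the medical monitor's review still operate, and extra DSMB meetings can be requested. This also stands, and it confines the issue to the last two infusions in at most five patients.

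On the arm labels, a reader might infer that naming Arm 2.1 in the dosing text assigns active product to the placebo arm. The documents do not support this. Arm 2.1 is defined nowhere, so it cannot simply be equated with Arm 2, and the Investigational Plan gives Arm 2 saline. The Randomization section's reference to allocation inside an arm suggests leftover text from a design in which each arm held both groups. The labels are an editorial fault and are not evidence of a dosing error.

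**Conclusion.** The internal contradiction is established. The severe cohort's day label is 7 days after the only scheduled third infusion and 1 day beyond the latest in-window fourth. That conclusion needs no assumption beyond the stated schedule and window.

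The consequence is conditional. It arises only if the board's meeting is set by the label and patients are dosed on schedule; then four of four infusions are given, against the two intended before review, in up to five severe patients. It is a flaw in the wording of an operative safety gate, worth correcting because the remedy is cheap. It does not show that the gate would fail. The documents do not settle whether the day or the schedule is the error, and this point takes no position on that.

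**What to change.** Reconcile the Data Safety Monitoring Board section with the protocol's dosing text, Table 2 and visit procedures, so that the stated day and the stated infusion agree for the severe cohort. If the label is meant as a study-calendar day, or if a separate schedule for severe patients was intended, the protocol should say so, and SAP section 2.2 should be brought into line where the infusion days differ. State explicitly that the review is triggered by the infusion events, if that is the intention.

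As a separate minor edit, replace the undefined arm labels in the dosing text with labels that match the two arms in the Investigational Plan.

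The cost is amendment wording and a check that the DSMB calendar follows the reconciled text. If only the day label changes, the sample size, endpoints and analysis are unaffected.
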